**Table 15      Toxicity Management Guidelines and Retreatment Criteria**

Event	Characteristic	Grade	Management recommendation
Anaemia, leucopenia, or neutropenia	Haemoglobin $\leq$ 9g/dL WBC $< 3 \times 10^9/L$ ANC $< 1.5 \times 10^9/L$	$\geq 2$	Hold [  Ac]-FPI-2068 (with or without FPI-2053) until improvement to Grade 1 or baseline. Dose may be held for up to 4 weeks beyond the next planned dose per CSP (i.e., beyond 56 days). Manage as deemed appropriate by Investigator. Use of growth factors is permitted but should be discontinued once the AE resolves to Grade 1 or baseline. Transfusions may be given as clinically indicated for anaemia.
Thrombocytopenia	Platelets: $> 50 \times 10^9/L$ and $< 75 \times 10^9/L$	2	Hold [  Ac]-FPI-2068 (with or without FPI-2053) until improvement to Grade 1 or baseline, retreat at the same dose level. Manage as deemed appropriate by Investigator. Transfusions may be given as clinically indicated for thrombocytopenia.
	Platelets: $< 50 \times 10^9/L$	3 and 4	Hold [  Ac]-FPI-2068 (with or without FPI-2053) until improvement to Grade 1 or baseline, reduce by one dose level. Manage as deemed appropriate by Investigator. Transfusions may be given as clinically indicated for thrombocytopenia.
Increased serum creatinine	CrCl 30-59 mL/min/1.73 m 	2	Hold [  Ac]-FPI-2068 (with or without FPI-2053) until improvement to Grade 1 or baseline. If resolved in $\leq 7$ days, then maintain dose level for the next cycle. If resolved in $> 7$ days, then reduce by one dose level for the next cycle. Manage as deemed appropriate by Investigator.
	CrCl 15-29 mL/min/1.73 m 	3	Treatment should be permanently discontinued.

Event	Characteristic	Grade	Management recommendation
	CrCl < 15-29 mL/min/1.73 m  ; dialysis or renal transplant indicated	4	Treatment should be permanently discontinued.
Increased AST or ALT	> 5.0 - 20 x ULN if baseline was normal; > 5.0 baseline if baseline was abnormal	3	Hold [  Ac]-FPI-2068 (with or without FPI-2053) until improvement to Grade 1 or baseline or ≤ Grade 2 if liver metastases are present. If resolved in ≤ 7 days, then maintain dose level for the next cycle. If resolved in > 7 days, then reduce by one dose level for the next cycle.
	> 20.0 × ULN if baseline was normal; > 20.0 × baseline if baseline was abnormal	4	Treatment should be permanently discontinued.

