Increased total bilirubin	> 3.0 - 10.0 × ULN if baseline was normal; > 3.0 - 10.0 × baseline if baseline was abnormal	3	Hold [  Ac]-FPI-2068 (with or without FPI-2053) until improvement to Grade 1 or baseline. If resolved in ≤ 7 days, then reduce by one dose level for the next cycle. If resolved in > 7 days, then permanently discontinue study drug
	> 10.0 × ULN if baseline was normal; > 10.0 × baseline if baseline was abnormal	4	Treatment should be permanently discontinued.
Non-haematologic AEs		3	Hold [  Ac]-FPI-2068 (with or without FPI-2053) until improvement to Grade 1 or baseline. If resolved < 7 days, then maintain dose level for the next cycle. If resolved > 7 days, then reduce by one dose level for the next

Event	Characteristic	Grade	Management recommendation
			cycle.
		4	Treatment should be permanently discontinued.
Infusion-related reaction		1	
The infusion rate may be decreased by 50% or temporarily interrupted until resolution of the event.
 
Monitor closely and manage per institutional standard at the discretion of Investigator.
 
If no other reactions appear, the subsequent infusion rate could be resumed at the initial planned rate.

		2	
Temporarily interrupt study intervention administration.
 
If the event resolves or improves, infusion can be restarted at a 50% reduced infusion rate.
 
Consider discontinuation if recurrent Grade 2 despite premedication and 50% reduced infusion rate.
 
Acetaminophen and/or antihistamines may be administered per institutional standard at the discretion of the Investigator.
 
Steroids should not be used for routine premedication of Grade <math>\leq 2</math> infusion-related reactions.
 
Consider appropriate premedication prior to subsequent doses (see Section 6.1.2).

		3-4	
Discontinue study intervention.
 
Manage severe infusion-related reactions per institutional standards (e.g., IM epinephrine, followed by IV diphenhydramine and famotidine, and IV glucocorticoid IV fluid therapy, oxygen inhalation etc).

ILD/pneumonitis		Any grade	
Please follow the dose modifications specific to each severity grade.
 
Closely monitor participants for signs and symptoms of pneumonitis or ILD (e.g., new onset or worsening shortness of

Event	Characteristic	Grade	Management recommendation

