### Non-haematologic AEs

- All cases of laboratory abnormalities that meet Hy's Law criteria
  - AST or ALT  $\geq 3 \times$  ULN and
  - total bilirubin  $\geq 2 \times$  ULN and
  - alkaline phosphatase  $< 2 \times$  ULN and
  - no other reason for liver injury
- $\geq$  Grade 3 non-haematologic toxicities except for the following:
  - Grade 3 nausea, vomiting or diarrhoea for less than 72 hours with adequate antiemetic and other supportive care
  - Grade 3 fatigue for less than 1 week
  - Grade 3 or higher electrolyte abnormality that lasts up to 72 hours, is not clinically complicated, and resolves spontaneously or responds to conventional medical intervention
  - Grade 3 or higher amylase or lipase that is not associated with symptoms or clinical manifestations of pancreatitis
  - Alopecia
- Any other toxicity that in the opinion of the Investigator represents a clinically significant hazard to the participant.
- Any death not clearly due to the underlying disease or extraneous causes.

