### **6.7.9 Dose Modifications**

If a participant experiences a clinically significant and/or unacceptable toxicity including a DLT not attributable to the disease or disease-related processes under investigation, dosing will be interrupted, delayed, or the dose reduced and supportive therapy administered as required (see [Table 15](#)).

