## **7 DISCONTINUATION OF STUDY INTERVENTION AND PARTICIPANT DISCONTINUATION/WITHDRAWAL**

### **7.1 Discontinuation of Study Intervention**

It may be necessary for a participant to permanently discontinue (definitive discontinuation) study intervention prior to completion of the Treatment Period. If study intervention is permanently discontinued, the participant will remain in the study to be evaluated for follow-up- assessments. See the SoA for the End of Treatment and Extended Follow-up period (see [Table 25](#)) for data to be collected at the time of discontinuation of study intervention and follow-up, and for any further evaluations that need to be completed.

Note that discontinuation from study intervention is NOT the same as withdrawal from the study (see Section [7.1.1](#)).

The participant should continue attending subsequent study visits and data collection should continue according to the CSP. If the participant does not agree to continue in-person study visits, a modified follow-up must be arranged to ensure the collection of endpoints and safety information. This could be a telephone contact with the participant at the Extended Safety Follow-up visit, a contact with a relative or treating physician, or information from medical records. The approach taken should be recorded in the medical records. A participant who agrees to modified follow-up is not considered to have withdrawn consent or to have withdrawn from the study.

Participants will continue to receive repeat cycles of treatment at the dose level and schedule of administration at which they were enrolled:

- up to a maximum of three cycles or
- until individual participant-specific cumulative radiation dose limits to specified organs based on [In]-FPI-2107 imaging are reached (see Section [4.3](#)).

Participants must also be discontinued from study treatment in the following situations:

- Unacceptable AE or inability to tolerate study therapy
- Delay in dosing of 28 days, without approval of Sponsor or Medical Monitor

- Documented, confirmed radiographic progressive disease (PD) (as assessed per RECIST 1.1)
  - Participants may remain on study treatment following confirmed radiographic PD if, in the opinion of the Investigator and with the agreement of the Sponsor and/or Medical Monitor, they continue to derive clinical benefit from the study treatment and if the following criteria are met:

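### Table 15 has no row for combined AST/ALT and bilirubin elevation, so part of the Hy's Law range leaves same-dose retreatment open after a confirmed DLT

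*Protocol*

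**What the plan says.** Section 6.7.7.1 lists among the non-haematologic DLTs "All cases of laboratory abnormalities that meet" Hy's Law criteria: AST or ALT ≥ 3 × ULN, total bilirubin ≥ 2 × ULN, ALP < 2 × ULN and no other reason for liver injury.

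Sections 8.5.6 and 6.7.9 and Appendix E 1 point to the toxicity management guidelines, that is Table 15, for what to do next. Appendix E 1 adds that the appendix is not meant as a full guide to managing raised liver tests.

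Table 15 (Section 6.7.3) contains these relevant rows:

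- **AST/ALT, Grade 3:** "> 5.0 - 20 x ULN if baseline was normal; > 5.0 baseline if baseline was abnormal". Hold; if resolved within 7 days, "then maintain dose level for the next cycle". Otherwise: "If resolved in $> 7$ days, then reduce by one dose level for the next cycle".
- **AST/ALT, Grade 4 (above 20 ×):** discontinue permanently.
- **Bilirubin, Grade 3 (above 3 to 10 ×):** hold; reduce one level if resolved within 7 days. Otherwise: "If resolved in > 7 days, then permanently discontinue study drug".
- **Bilirubin, Grade 4 (above 10 ×):** discontinue permanently.
- **Other non-haematologic events, Grade 3:** hold; "If resolved < 7 days, then maintain dose level for the next cycle", with a reduction if slower. Grade 4: discontinue permanently.

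After a DLT, Section 6.7.9 says "dosing will be interrupted, delayed, or the dose reduced and supportive therapy administered as required", with a reference to Table 15. Section 7.1 sets the default: "Participants will continue to receive repeat cycles of treatment at the dose level and schedule of administration at which they were enrolled", up to three cycles.

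**The concern.** Hy's Law is defined by two analytes rising together. Table 15 grades each one alone, and its rows start above the Hy's Law thresholds: above 5 × against 3 × ULN for transaminases, and above 3 × against 2 × ULN for bilirubin. A case can therefore be a DLT by definition and still fall where the table sets no action, or sets a hold followed by the same dose.

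The result is also out of step with the rest of the table. At normal baseline, an isolated bilirubin above 3 × ULN always leads to a reduction or discontinuation. Grade 3 creatinine and Grade 2 pneumonitis lead to discontinuation.

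The liver matters here. Table 5 lists hepatic disorders as a clinically significant risk and names the toxicity management guidelines as one of the mitigations. In Table 10 the liver has the largest projected absorbed dose of the four critical organs, both without predosing (3.6 Sv) and with it (1.5 Sv). At stake is whether a participant who recovers from confirmed drug-induced Hy's Law may be given the same dose again.

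**Working it through.** There is no sample-size or probability figure to reproduce. The check applies the Table 15 liver rows across the Hy's Law range, then looks for any other provision that closes what they leave open.

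**Step 1: liver rows, normal baseline.** Take the strictest applicable row, and assume both analytes resolve in the same time class.

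| AST/ALT (× ULN) | Bilirubin (× ULN) | Resolved in ≤ 7 days | Resolved in > 7 days |
|---|---|---|---|
| 3–5 | 2–3 | no liver row | no liver row |
| above 5 to 20 | 2–3 | hold, same dose | hold, one level down |
| 3–20 | above 3 to 10 | hold, one level down | discontinue |
| above 20, or any with bilirubin above 10 | 2 or more | discontinue | discontinue |

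The open zone is (a) the first line, and (b) the second line when resolved within 7 days.

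**Step 2: abnormal baseline.** The thresholds become multiples of baseline (reading the AST/ALT entry as 5.0 × baseline). Two illustrations:

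- AST at 2 × and bilirubin at 1.2 × ULN: no liver row applies up to 5 × 2 = 10 × ULN for AST and 3 × 1.2 = 3.6 × ULN for bilirubin.
- Upper limits of inclusion criterion 10 with liver metastases (AST 5 ×, bilirubin 1.5 × ULN): no liver row up to 5 × 5 = 25 × and 3 × 1.5 = 4.5 × ULN.

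An alternative cause is likelier in such participants, and with one the case is not Hy's Law.

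**Step 3: time available to recover.** Cycle 1 visits fall on Days 8, 15, 22, 29 and 36, and the next dose is due no earlier than Day 57.

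- Zone (a) has no 7-day clock. A case found between Day 8 and Day 36 has 57 − 8 = 49 down to 57 − 36 = 21 days to recover before the earliest next dose. Section 6.7.9 still applies in that time.
- Zone (b) requires recovery within 7 days, about one visit interval (15 − 8 = 7). Slower recovery forces a reduction.

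**Step 4: other provisions.**

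- **Section 6.7.9** compels an action after a DLT, but offers three alternatives. Only one lowers the dose. A delay followed by the same dose complies.
- **Table 24, footnotes c and e,** ask for tests within eligibility limits and for related events to have resolved before redosing. They govern when treatment may resume and leave the dose level open.
- **The generic non-haematologic rows** need a graded event. Grade 4 stops treatment, and Grade 3 resolving in more than 7 days reduces the dose. Grade 3 resolving in under 7 days keeps it. The protocol assigns no grade to a Hy's Law case.
- **Section 7.1** mandates discontinuation for an unacceptable adverse event, but does not say that Hy's Law is one.
- **Appendix E 4.2 and E 5** require an SAE report within 1 day, Study Physician contact and a sponsor-level review. For a confirmed case the stated outcome is the report term and a related causality. No dosing instruction follows.
- **Appendix B 3** says the sponsor would not normally support re-challenge. The remark sits in a guide to judging causality.

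None of these rules out the same dose after recovery and a delay.

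**Cross-reference.** Sections 8.5.6 and E 1 cite Section 6.7.2, which states only that FPI-2053 doses are not modified within a participant. E 1 also names Table 15.

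**The case against.** The best reply is that the zone is regulated even though the liver rows miss it. Section 6.7.9 makes action after a DLT mandatory. Section 7.1 says participants must stop for an unacceptable event. Any confirmed case goes through a review that includes the Global Clinical Lead and the Global Safety Physician. Table 15 is itself a set of guidelines that the Investigator, Sponsor and Medical Monitor may adjust by agreement (Section 6.7.3). Same-dose retreatment would have to pass all of that, and zone (b) needs a large transaminase rise to clear within a week.

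Most of this stands, and it defeats two stronger readings. A reader might infer that dosing may simply continue unchanged after a Hy's Law DLT; Section 6.7.9 and the Table 24 footnotes exclude that. A reader might also infer that stopping rests on discretion alone. Section 7.1 makes it mandatory once the event is judged unacceptable, and a Grade 4 rating does so under Table 15. Counting how many combinations in the Step 1 table end in the same dose would not measure size either: recovery time has no effect in several of them, a Grade 3 or 4 rating could change the outcome, and no frequencies are given.

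What the reply does not supply is a rule for the case in question. Whether the event is unacceptable, how it is graded and what the review concludes about dosing are all left to judgement, while the explicit instruction in zone (b) is to keep the dose.

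It can also be said that permanent discontinuation goes beyond the gap, since some confirmed cases now get a reduced dose. That is a fair benefit-risk point in participants without further effective standard therapy, and it is counted as a cost under the fix.

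**Conclusion.** The concern holds in this limited form. In a defined part of the Hy's Law range, Table 15 either has no liver row or directs the same dose, and no other provision excludes same-dose retreatment once a confirmed case has recovered and dosing has been delayed. At normal baseline the zone is AST/ALT 3–5 × with bilirubin 2–3 × ULN, plus AST/ALT above 5 to 20 × with bilirubin 2–3 × ULN resolved within 7 days. It is wider at abnormal baseline.

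This rests on taking the strictest applicable liver row, on both analytes resolving in the same time class, and on the event not being graded 4 or judged unacceptable. How often it would arise cannot be estimated from the protocol.

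The effect is on the individual participant. The DLT still enters the mTPI-2 decision, so cohort escalation is unaffected. It should be fixed in the next amendment.

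**What to change.** Add a row to Table 15 that overrides the single-analyte rows:

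- **Trigger:** AST or ALT ≥ 3 × ULN with total bilirubin ≥ 2 × ULN, in any cycle.
- **Action:** hold pending the Appendix E review; discontinue permanently if no alternative cause is found; if an alternative cause is agreed, follow the single-analyte rows.

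In Sections 8.5.6 and E 1, change the reference from 6.7.2 to 6.7.3/Table 15.

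The cost is one row and two cross-references. No new tests are needed, because Table 29 already requires AST, ALT, ALP and bilirubin to be assessed concurrently. The clinical cost is that a few recovered participants with confirmed Hy's Law, including some who would now be retreated at a reduced dose, lose up to two further cycles (three planned minus the one already given).

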#### **6.7.4 Starting Dose, Dose Escalation Scheme, and Stopping Criteria**

Part A Cohort 1 and Cohort 2 will be initiated simultaneously and enrol in parallel.

Participants will be assigned in an alternating manner. The first participant in Cohort A2 will be treated with [Ac]-FPI-2068 only after the first participant in Cohort A1 has undergone a minimum of one week of safety observation. Dosing of [Ac]-FPI-2068 in Part A will be 15 kBq/kg/cycle and be administered at this dose for up to a maximum of 3 cycles. If FPI-2053 is to be administered prior to [Ac]-FPI-2068 or FPI-2107 then the interval between the administration of FPI-2053 and FPI-2068 or [In]-FPI-2107 will be 30 minutes to 2 hours. Following review of safety, PK, biodistribution, and dosimetry data from Cohorts A1 and A2 by the Sponsor and the SRC, Cohort A3 may be initiated if deemed necessary.

In Part B there will be a minimum of 56 days between completion of dosing in the last evaluable participant, for a dose escalation decision, from one cohort and the start of dosing in the subsequent cohort.

There may be ongoing participants who become evaluable after the dose escalation decision (i.e., dosing may start in the next cohort whilst these participants are ongoing).

Intra-participant dose escalation is not permitted.

The dose for subsequent cohorts or a decision to stop recruitment will be agreed by the SRC after review of the data from each cohort (see Section [6.7.8](#)).

In Part B a minimum of three and a maximum of nine participants will be enrolled at a given dose level.

Part B, dose escalation to the next dose level will be conducted using the mTPI-2 algorithm with a target DLT rate of 30% and an equivalence interval (25%, 35%). A minimum of 3 participants must complete the DLT-evaluation period before making an escalation decision. Dose escalation will consist of four planned dose levels. Intermediate dose levels may be

explored if warranted by emerging safety, PK, pharmacodynamic, biomarker, and efficacy data. Dose escalation and de-escalation will follow the mTPI-2 algorithm schema below:

- A minimum of 3 evaluable participants are required in each dose level unless unacceptable toxicity is encountered in the first 2 subjects prior to enrolment of the third participant, which would require dose de-escalation per the mTPI-2 design.
- If a de-escalation decision is made, choice of de-escalation to the previous dose level will be at the discretion of the SRC. In the eventuality that a decision is made to de-escalate back to a dose escalation level that was previously deemed safe, and into which participants have since been enrolled at that dose level, these participants will now be included in further dose escalation decisions following mTPI-2 rules.
- If a stay (“S”) decision is made, additional participants will be enrolled for a given dose level (typically in groups of 2 to 4 participants).
- Administration of the first dose of investigational product will be staggered by a minimum of 24 hours between the first and second participants in each dose escalation cohort.
- At the discretion of the Sponsor, dose escalation may be stopped before an MTD is reached. In this case, the dose for evaluation in any future dose expansion study may be chosen based on an assessment of PK, pharmacodynamics, safety, or efficacy data.
- The MTD will be determined by isotonic transformation of posterior mean DLT rates observed during dose escalation using the mTPI-2 method ([Ji et al, 2010](#)).

The mTPI-2 algorithm employs a simple beta-binomial Bayesian model. The posterior density of the toxicity probability is divided into multiple intervals with equal length. These intervals are categorised as underdosing, proper dosing, and overdosing in terms of toxicity. The underdosing interval corresponds to a dose escalation, overdosing corresponds to a dose de-escalation, and proper dosing corresponds to staying at the current dose. Given an interval and a probability distribution, the unit probability mass of that interval is defined as the probability of the interval divided by the length of the interval. The design for the dose escalation phase of the study uses a target DLT rate of 30% and an equivalence interval (25%, 35%) for dose escalation/de-escalation decisions as well as MTD determination. A dose level will be considered unsafe, with no additional participants enrolled at that dose level, if it has an estimated 95% or more probability of exceeding the target DLT rate of 30% (i.e.,  $P[DLT > 30\% \text{ data}] \geq 95\%$ ) with at least 3 participants treated and evaluated at that dose level. In [Table 16](#), dose escalation/de-escalation decision rules are computed based on the above information.

**Table 16** **mTPI-2 Decision Rules**

Number	Number of participants treated at current dose level
--------	--

**Table 16** mTPI-2 Decision Rules

Number	Number of participants treated at current dose level								
	1	2	3	4	5	6	7	8	9
0	S a	S a	E	E	E	E	E	E	E
1	S b	S b	S	S	E	E	E	E	E
2		DU	D	D	D	S	S	S	E
3			DU	DU	D	D	D	D	S
4				DU	DU	DU	D	D	D
5					DU	DU	DU	DU	DU
6						DU	DU	DU	DU
7							DU	DU	DU

D, de-escalate to the next lower dose level; DLT, dose limiting toxicity; DU, current dose is unacceptably toxic; E, escalate to the next higher dose level; EI, equivalence interval; mTPI, modified toxicity probability interval; S, stay at the current dose level.

a Changed from “E” to “S” as a minimum of 3 evaluable participants are needed to make a dose escalation decision.

b Changed from “D” to “S” as a minimum of 3 evaluable participants are needed to make a dose escalation decision.

Target toxicity (%) is 30% and EI (25%, 35%); Sample size cap for each dose level will be nine participants.

Source(s): Modified from [\(Ji et al, 2010; Guo et al, 2017\)](#).

#### 6.7.4.1 Stopping Criteria

The study will be suspended if any death or two Grade 4, non-haematologic adverse reactions within the same organ system are observed. These should be at least potentially related to the investigational products, and not related to disease progression or intercurrent illness.

Continuation of the study may occur if deemed appropriate by the SRC and may require a protocol amendment. Participants on treatment at time of suspension may continue if they are tolerating treatment well, and if continuing treatment is considered appropriate for the toxicity in question based upon the treating physician’s medical judgement. Dose reduction may also be considered.

